## **Protocol Version Record**

Version 1.0	January 25, 2016
Version 2.0	January 26, 2016
Version 3.0	January 31, 2016
Version 4.0	February 2, 2016
Version 5.0	February 14, 2016
Version 6.0	March 4, 2016
Version 7.0	March 7, 2016
Version 8.0	April 8, 2016
Version 9.0	April 19, 2016
Version 10.0	April 24, 2016
Version 11.0	April 26, 2016
Version 12.0	May 16, 2016
Version 13.0	June 26, 2017
Version 14.0	July 30, 2017
Version 15.0	October 9, 2017
Version 16.0	October 26, 2017
Version 17.0	November 8, 2017

## **Protocol Summary**

**Title:** Apixaban for Primary Prevention of Venous Thromboembolism in Patients with Multiple Myeloma Receiving Immunomodulatory Therapy

**Design:** U.S.-based, single-center, single-arm, open-label, proof-of-concept study

**Brief Treatment Description:** Direct anti-factor Xa inhibition with apixaban 2.5 mg orally twice daily for primary prevention of VTE

**Purpose:** To determine the rate of major and clinically relevant non-major bleeding and the rate of symptomatic VTE in MM patients on immunomodulatory drugs (IMiDs) who are receiving apixaban 2.5 mg orally twice daily. This study will provide event rates that could inform the design of a larger randomized controlled trial.

**Population:** Outpatients with MM receiving IMiDs (i.e., thalidomide [Thalomid], lenalidomide [Revlimid], and pomalidomide [Pomalyst]).

**Enrollment:** 50 subjects

**Clinical Site Locations:** 1 center (Vanderbilt University Medical Center)

**Study Duration:** 22 months; enrollment period of up to 16 months with 6-month follow-up.

### **Primary Safety and Efficacy Outcomes:**

**Primary Safety Outcome:** The 6-month rate of International Society on Thrombosis and Haemostasis major and clinically relevant non-major bleeding in MM patients receiving IMiDs who are prescribed apixaban 2.5 mg orally twice daily for primary prevention of VTE.

**Secondary Safety Outcome:** All-cause mortality at 6 months will be recorded. Cause of death will be classified as related to cancer, myocardial infarction, PE, or other disease state.

**Primary Efficacy Outcome:** The 6-month rate of symptomatic VTE in MM patients receiving IMiDs who are prescribed apixaban 2.5 mg orally twice daily for primary prevention of VTE.

**Secondary Efficacy Objectives:** The 6-month rate of myocardial infarction and stroke will also be calculated.

**Follow-Up:** Follow-up will consist of Electronic Health Record review at 6-months from study enrollment.

**Study Flow Diagram**

IMiDs, immunomodulatory drugs; VTE, venous thromboembolism

## **Abbreviations and Definitions**

*Listed in alphabetical order*

DVT, deep vein thrombosis

eCRF, electronic case report form

IMiDs, immunomodulatory drugs (i.e., thalidomide [Thalomid], lenalidomide [Revlimid], and pomalidomide [Pomalyst])

ISTH, International Society on Thrombosis and Haemostasis

LMWH, low-molecular weight heparin

MM, multiple myeloma

NOACs, non-vitamin K oral anticoagulants

PE, pulmonary embolism

PI, Proteasome inhibitors

SAE, significant adverse event

UADE, unanticipated adverse drug effect

VTE, venous thromboembolism

## **Specific Aims**

Patients living with multiple myeloma (MM) have an increased risk of venous thromboembolism (VTE) due to the disease itself and the use of targeted therapies, including immunomodulatory drugs (IMiDs). Prevention of VTE has become a major management challenge during MM treatment. There is a paucity of data with respect to the non-vitamin K oral anticoagulants (NOACs) in the cancer population. However, the NOACs offer comparable efficacy but improved safety compared with warfarin. Apixaban has shown excellent safety and efficacy for treatment and prevention of recurrent VTE (1,2). The safety and efficacy of apixaban for primary prevention of VTE in MM patients has not been established.

**Aim #1:** To quantify the 6-month rate of major and clinically relevant non-major bleeding in MM patients receiving IMiDs who are prescribed apixaban 2.5 mg orally twice daily for primary prevention of VTE.

**Hypothesis #1:** The 6-month rate of major and clinically relevant non-major bleeding in MM patients receiving IMiDs who are prescribed apixaban 2.5 mg orally twice daily for primary prevention of VTE will be  $\leq 3\%$  (2). Although the MM population, in general, has a higher medical acuity than that of the previous large randomized controlled trials of apixaban, we will be selecting a stable population of MM patients who are appropriate for immunomodulatory therapy.

**Aim #2:** To quantify 6-month rate of symptomatic VTE in MM patients receiving IMiDs who are prescribed apixaban 2.5 mg orally twice daily for primary prevention of VTE.

**Hypothesis #2:** The 6-month rate of symptomatic VTE in MM patients receiving IMiDs who are prescribed apixaban 2.5 mg orally twice daily for primary prevention of VTE will be  $< 7\%$  (3). Although additional therapies for MM such as dexamethasone and erythropoietin-stimulating agents may further increase the risk of VTE, the rate of incident VTE should be reduced to  $< 7\%$  with apixaban.

## **Introduction and Background**

Multiple myeloma (MM) is a plasma cell malignancy characterized by clonal proliferation of malignant plasma cells in the bone marrow microenvironment, monoclonal protein in the blood or urine, and associated organ dysfunction (4). Overall survival has improved due to the advent of novel targeted therapies, including immunomodulatory drugs (IMiDs) and proteasome inhibitors (PIs). As with other hematological malignancies, MM is associated with an increased risk of venous thromboembolism (VTE). The risk of VTE is further increased in the setting of IMiDs. Currently used IMiDs include thalidomide (Thalomid), lenalidomide (Revlimid), and pomalidomide (Pomalyst). A meta-analysis of more than 3000 MM patients showed that the risk of VTE increased nearly 3-fold when the IMiD thalidomide was prescribed and nearly 8-fold when thalidomide was combined with other chemotherapeutics (5). The risk of VTE is amplified when IMiDs are combined with a novel proteasome inhibitor, carfilzomib, that was recently approved by the U.S. Food and Drug Administration (6). Due to the increasing use of IMiD-based regimens, prevention of VTE has become a major management challenge during MM treatment (**Table 1**) (7). A systematic analysis of MM patients treated with IMiDs, especially in combination with other therapies, shows that VTE risk remains an important complication in this population ([name] and [name], unpublished data).

**Table 1.** VTE incidence in IMiDs trials (7).

Treatment Regimen	VTE incidence (%) without thromboprophylaxis	VTE incidence (%) with thromboprophylaxisa
Thalidomide		
Alone	2-10	NA
Plus dexamethasone	2-26	8-25
Plus chemotherapy b	3-58	3-31
Lenalidomide		
Alone	0-33	NA
Plus dexamethasone	8-75	3-14
Plus chemotherapy b	14	5-9
Pomalidomide		
Alone	NA	2
Plus dexamethasone	NA	2-5

VTE, venous thromboembolism; NA, not applicable

aAspirin (81-325mg daily), low molecular weight heparin (LMWH), fixed warfarin (1-1.25mg daily) and full-dose of warfarin (target INR 2-3) have been used for prophylaxis. Choice of thromboprophylaxis was largely based on physicians' discretion.

bThalidomide and lenalidomide were used in combination with other therapeutic agents, including melphalan, doxorubicin and cyclophosphamide.

MM patients also have a higher risk of arterial thromboembolic events, including myocardial infarction and stroke (7). IMiDs also appear to increase the risk for arterial thromboembolic events. In the long-term follow-up of 704 MM patients in two phase 3, randomized clinical trials, the frequency of myocardial infarction and cerebrovascular events were 1.98% and 3.4%, respectively, in patients treated with lenalidomide and dexamethasone compared with 0.57% and 1.7%, in patients treated with dexamethasone alone (<https://www.gov.uk/drug-safety-update/lenalidomide-risk-of-thrombosis-and-thromboembolism>). Lenalidomide carries a black box warning of significant myocardial infarction and stroke risks in MM patients receiving lenalidomide and dexamethasone treatment.

Currently, there are no guidelines regarding the optimal thromboprophylactic regimen for MM patients receiving IMiDs. A broad-based VTE prevention guideline for cancer patients is too general to be of practical use in MM patients (8). In the case of MM, aspirin (81-325 mg daily), low-molecular weight heparin (LMWH), and warfarin (target INR 2-3) have all been prescribed for VTE prophylaxis. However, the specific prophylactic regimen is ultimately based on the treating clinician's best clinical judgment (7,9). The choice of VTE prophylaxis is further complicated due to frequent renal dysfunction in MM patients. Furthermore, these patients are often reluctant to undertake an extended duration prophylactic LMWH regimen of daily self-injections due to anxiety and injection-site discomfort. An unintended consequence of LMWH injections is that injectable prophylactic anticoagulant regimens are associated with decreased medication adherence (10).

There is a paucity of data with respect to the non-vitamin K oral anticoagulants (NOACs) in the cancer population. However, the NOACs have been shown to offer comparable efficacy but improved safety compared with warfarin. Apixaban has shown excellent safety and efficacy for treatment and prevention of recurrent VTE (1,2).

In a randomized, double-blind study (AMPLIFY), apixaban (administered as a loading dose of 10 mg twice daily for 7 days, followed by 5 mg twice daily) was compared with subcutaneously-administered enoxaparin followed by warfarin in 5395 patients with acute venous thromboembolism (1). The primary efficacy outcome of recurrent symptomatic VTE or VTE-related death occurred in 59 of 2609 patients (2.3%) in the apixaban group compared with 71 of 2635 (2.7%) in the warfarin group (relative risk, 0.84; 95% confidence interval [CI], 0.60 to 1.18;  $p < 0.001$  for non-inferiority). Major bleeding occurred in 0.6% of patients who received apixaban and in 1.8% of those who received warfarin (relative risk, 0.31; 95% CI, 0.17 to 0.55;  $p < 0.001$  for superiority). A composite outcome of major bleeding and clinically relevant nonmajor bleeding occurred in 4.3% of the

patients in the apixaban group compared with 9.7% of those in the conventional-therapy group (relative risk, 0.44; 95% CI, 0.36 to 0.55;  $p < 0.001$ ).

In the randomized, double-blind AMPLIFY-EXT study, two doses of apixaban (2.5 mg and 5 mg, twice daily) were compared with placebo in patients with VTE who had completed 6 to 12 months of anticoagulation therapy and for whom there was clinical equipoise regarding the continuation or cessation of anticoagulation therapy (2). A total of 2486 patients underwent randomization. Symptomatic recurrent venous thromboembolism or death from venous thromboembolism occurred in 73 of the 829 patients (8.8%) who were receiving placebo versus 14 of the 840 patients (1.7%) who were receiving 2.5 mg of apixaban and 14 of the 813 patients (1.7%) who were receiving 5 mg of apixaban ( $p < 0.001$  for both comparisons). The rate of major and clinically relevant non-major bleeding in patients receiving apixaban 2.5 mg orally twice daily for extended-duration prevention of recurrent VTE was similar to that of placebo.

Though the stroke prevention in atrial fibrillation population is different, the AVERROES Trial also demonstrated the strong safety profile of apixaban, which had the same major bleeding rate as aspirin (11).

### **Rationale for the Proposed Study**

MM is associated with an increased risk of venous thromboembolism (VTE). The use of targeted therapies, including immunomodulatory drugs (IMiDs), has improved outcomes for patients with MM but also increases the risk of VTE. Prevention of VTE has become a major management dilemma during MM treatment. There is a paucity of data with respect to the non-vitamin K oral anticoagulants (NOACs) in the cancer population, including patients with MM. However, the NOACs have been shown to offer comparable efficacy but improved safety compared with warfarin. Apixaban has shown excellent safety and efficacy for treatment and prevention of recurrent VTE (1,2). Compared with injectable thromboprophylactic regimens such as enoxaparin, apixaban offers the advantages of being orally administered and less reliant on renal clearance. The safety and efficacy of apixaban for primary prevention of VTE in MM patients has not been established. The current study will evaluate apixaban (2.5 mg twice daily) in a patient population without a history of prior VTE. Although the current study population is high risk for VTE, it is likely to be lower risk for VTE than those of the prior randomized controlled trials of apixaban for secondary prevention. Furthermore, current practice is to provide MM patients receiving IMiDs with prophylactic doses (not treatment doses) of low-molecular weight heparin (such as enoxaparin 40 mg injected daily). Accordingly, the rationale to test apixaban (2.5 mg twice daily) is consistent with the standard practice of prophylactic anticoagulation.

The current study will provide event rates that will inform the design of a larger randomized controlled trial. If safe and effective, apixaban will satisfy a critical unmet need and will represent a substantial advance and “game changer” in the prevention of VTE in this high risk patient population.

### **Study Objectives**

**Primary Safety Objective:** To quantitatively assess the 6-month rate of major and clinically relevant non-major bleeding in MM patients receiving IMiDs who are prescribed apixaban 2.5 mg orally twice daily for primary prevention of VTE.

**Primary Efficacy Outcome:** To quantitatively assess the 6-month rate of symptomatic VTE in MM patients receiving IMiDs who are prescribed apixaban 2.5 mg orally twice daily for primary prevention of VTE.

**Secondary Efficacy Outcome:** To quantitatively assess the 6-month rate of myocardial infarction and stroke.

### **Study Design**

50-patient U.S.-based, single-center, single-arm, open-label, proof-of-concept study of apixaban 2.5 mg orally twice daily for primary prevention of VTE.

### **Study Duration**

The study will be completed in 24 months: 3 months for start-up (including Human Research Committee approval, hiring of additional staff, and finalizing the Case Report Form), 18 months for patient enrollment and data collection, and 3 months for data analysis and writing up the results (**Table 2**).

**Table 2.** Study timeline.

Milestone	Duration (months)
Start-up	3
Patient enrollment	12
Completion of data collection	6
Data analysis and completion of study report	3
TOTAL	24

### **Study Population**

Patients who are > 18 years of age or older with newly diagnosed MM, relapsed MM, MM on maintenance therapy and receiving IMiDs (i.e., thalidomide [Thalomid], lenalidomide [Revlimid], and pomalidomide [Pomalyst]).

### **Study Inclusion Criteria**

- Men and women
- Age > 18 years
- Current or prior diagnosis of symptomatic MM based on International Myeloma Working Group (IMWG) guidelines (<http://imwg.myeloma.org/category/guidelines-2/>) and will be starting or already receiving IMiD therapy with thalidomide [Thalomid], lenalidomide [Revlimid], or pomalidomide [Pomalyst]
- IMiD therapy given in the setting of newly diagnosed MM, relapsed MM, progressive MM, maintenance therapy or consolidation therapy as per IMWG criteria

**Patients must have had measurable disease as defined by at least one of the following\*\*:**

- Serum M-protein  $\geq 0.5$  g/dL by serum electrophoresis (SPEP) or for IgA myeloma, by quantitative IgA (>750 mg/dl)
- Urinary M-protein excretion at least 200 mg/24 hours
- Serum Free Light Chain (FLC) whereby the involved light chain measures  $\geq 10$  mg/dL and with an abnormal light chain ratio.

\*\*The patient must have met criteria for measurable disease at some point. Criteria do not have to be met at time of enrollment.

- Willing to provide written informed consent
- Eastern Cooperative Oncology Group (ECOG) functional status  $\leq 2$
- Providers must plan to treat the patient with IMiD therapy for a minimum of 6 cycles

### **Study Exclusion Criteria**

- Pregnancy
- Breastfeeding
- Women of child-bearing potential who are unwilling or unable to use an acceptable method of birth control (such as oral contraceptives, other hormonal contraceptives [vaginal products, skin patches, or implanted or injectable products], or mechanical products such as an intrauterine device or barrier methods [diaphragm, condoms, spermicides]) to avoid pregnancy for the entire study
- Any prior venous thromboembolism
- Contraindication to anticoagulant therapy

- Conditions for which serious bleeding may occur including:
  - Current or within last 6 months: intracranial bleeding, intraocular bleeding, gastrointestinal bleeding, endoscopically documented ulcer disease
  - Current or within last month: head trauma or other major trauma, major surgery
  - Current or within last 2 weeks: stroke, neurosurgical procedure
  - Current: gross hematuria, major unhealed wound, major surgery planned during the trial period, intracranial mass, vascular malformation, or aneurysm, overt bleeding, blood dyscrasia
  - CNS involvement of MM or other history of CNS malignancy
- Active and clinically significant liver disease
- Uncontrolled hypertension: systolic blood pressure >180 mm Hg or diastolic blood pressure >100 mm Hg
- Current endocarditis
- Requirement for ongoing anticoagulant therapy, including mechanical heart valve replacement and atrial fibrillation
- Severe valvular heart disease, including rheumatic heart disease and mitral stenosis
- Bioprosthetic heart valve replacement
- Requirement for dual antiplatelet therapy or single agent antiplatelet therapy with clopidogrel, prasugrel, or ticagrelor
- Requirement for aspirin at a dose higher than 165 mg daily.
- Hemoglobin < 9 mg/dL at time of screening
- Platelet count < 100,000/mm^3 at time of screening
- Serum calculated creatinine clearance (CrCl) < 25 ml/m at time of screening
- Alanine aminotransferase or aspartate aminotransferase level > 2 times the upper limit of the normal at time of screening
- Total bilirubin level > 1.5 times the upper limit of the normal at time of screening
- Life expectancy < 12 months or hospice care
- Prisoners or subjects who are involuntarily incarcerated
- Subjects who are compulsorily detained for treatment of either a psychiatric or physical (e.g., infectious disease) illness
- Receiving concurrent non-FDA-approved or investigational agents or has received an investigational agent within the past 30 days prior to the first dose of study treatment (with the exception of approved medications being used for an approved indication, e.g., investigating a new dosing regimen for an approved indication).
- Any condition, which in the opinion of the investigator, would put the subject at an unacceptable risk from participating in the study
- Any other medical, social, logistical, or psychological reason, which in the opinion of the investigator, would preclude compliance with, or successful completion of, the study protocol

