## **Safety Outcomes**

### **Primary Safety Outcome**

The primary safety outcome is the 6-month rate of major and clinically relevant non-major bleeding in MM patients receiving IMiDs who are prescribed apixaban 2.5 mg orally twice daily for primary prevention of VTE.

Using the ISTH classification, bleeding is defined as major if it is overt and associated with a decrease in the hemoglobin level of 2 g/dL or more, requires the transfusion of 2 or more units of blood, occurs into a critical site, or contributes to death (12).

Using the ISTH classification, clinically relevant nonmajor bleeding is defined as overt bleeding not meeting the criteria for major bleeding but associated with medical intervention, surgical intervention, or interruption of the study drug.

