## Subject Retention, Withdrawal, and Termination

Continued participation of study subjects will be encouraged at the time of outpatient evaluation through the 6-month follow-up interval. However, study subjects will be informed that they retain the right to withdraw from the study at any time without compromise to their current or subsequent medical care. Subjects will be terminated from the study if they expire or elect to withdraw.

If study subjects elect to withdraw, they will be asked for permission to do the following:

1. Be contacted by telephone **AND**
2. Have a family member contacted **AND**
3. Have their physicians contacted

Withdrawal criteria will include:

1. Patient requests to withdraw
2. Reasons related to SAE:
  - a. Initiating or continuing study drug places the subject at undue hazard as determined by the Investigator;
  - b. SAE or other safety concern that is related to study drug treatment;
  - c. Major or life-threatening bleeding (as defined in the protocol)
  - d. ALT or AST  $\geq 3$  ULN, if suspected to be due to the study drug
  - e. Calculated CrCL decreased to  $< 30$  mL/min confirmed by repeat testing at least one week later, or need for dialysis
  - f. Subjects in whom multiple myeloma is felt to be refractory to therapy or who have transitioned to a palliative treatment strategy
3. Pregnancy;
4. Patient develops severe hepatic impairment (Child-Pugh class C) during the trial;

5. Death;
6. Lost to follow-up (every attempt will be made by the Investigator not to have subjects “lost to follow-up”);
7. Study terminated by sponsor (termination of all or part of the study by the sponsor, in concert with the study leadership)

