	
malformation, or aneurysm, overt bleeding, blood dyscrasia
 
 Active and clinically significant liver disease
 
 Uncontrolled hypertension: systolic blood pressure >180 mm Hg or diastolic blood pressure >100 mm Hg
 
 Current endocarditis
 
 Requirement for ongoing anticoagulant therapy including mechanical heart valve replacement and atrial fibrillation
 
 Severe valvular heart disease, including rheumatic heart disease and mitral stenosis
 
 Bioprosthetic heart valve replacement
 
 Requirement for dual antiplatelet therapy or single agent antiplatelet therapy with clopidogrel, prasugrel, or ticagrelor
 
 Requirement for aspirin at a dose higher than 165 mg daily.
 
 Hemoglobin < 9 mg/dL
 
 Platelet count < 100,000/mm^3
 
 Calculated creatinine clearance (CrCl) < 25 ml/m
 
 Alanine aminotransferase or aspartate aminotransferase level > 2 times the upper limit of the normal
 
 Total bilirubin level > 1.5 times the upper limit of the normal
 
 Life expectancy < 12 months or hospice care
 
 Prisoners or subjects who are involuntarily incarcerated
 
 Subjects who are compulsorily detained for treatment of either a psychiatric or physical (eg, infectious disease) illness
 
 Receiving concurrent investigational agents or has received an investigational agent within the past 30 days prior to the first dose of study treatment (with the exception of approved medications being used for an approved indication, e.g., investigating a new dosing regimen for an approved indication).
 
 Any condition, which in the opinion of the investigator, would put the subject at an unacceptable risk from participating in the study
 
 Any other medical, social, logistical, or psychological reason, which in the opinion of the investigator, would preclude compliance with, or successful completion of, the study protocol

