Chronic liver disease (as noted in chart)	 Yes  No If yes, cirrhosis  yes  no
History of falls	 Yes  No
Cigarette smoking (check only 1)	 Current smoker  Former smoker  Never smoker
Major surgery within the past 3 months	 Yes  No If yes, date      MM      /      DD      /      YYYY  If within the last month, patient should not be enrolled.
Prior hospitalization within 30 days	 Yes  No
COPD	 Yes  No
Diabetes mellitus (Type I or II)	 Yes  No
Serum creatinine > 2.5 mg/dL	 Yes  No If yes, is patient on dialysis?  Yes

	
 No
 
If yes, patient should not be enrolled.
 
If no, creatinine clearance (Cockcroft-Gault) = ___ mg/dL

Concomitant medications	
 aspirin If yes, dose = ___ mg/daily
 
If > 165 mg/daily, patient should not be enrolled.
 
 daily NSAID use

Prior thromboprophylaxis regimen	
 Yes  No
 
If yes, check all that apply:
 
 LMWH  Fondaparinux  Unfractionated heparin  Warfarin  NOAC  Aspirin  Other: _____

Study Treatment	
Date study drug started	
___ / ___ / ___ MM DD YYYY

Date study drug stopped	
___ / ___ / ___ MM DD YYYY
 
Completed full 6 months of study drug?  Yes  No
 
If did not stay on drug for 6 months, reason why not?  Fulfilled criteria for a primary study outcome (VTE or major/clinically relevant non-major bleed)  Patient expired  Adverse drug event or side-effect  Change in clinical status (such as change in goals of care, comfort measures, hospice care)  Patient preference/withdrawal of consent

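### The hemoglobin exclusion is printed in mg/dL, so read literally it excludes nobody, and the CRF labels creatinine clearance in mg/dL and asks for its value in only some patients

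*Combined protocol and SAP*

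**What the plan says.** **Hemoglobin.** The Study Exclusion Criteria give "Hemoglobin < 9 mg/dL at time of screening". The screening page of the Case Report Form carries the same limit, "Hemoglobin < 9 mg/dL", and tells staff not to enroll if any exclusion is present. Under Primary Safety Outcome, one route to a major bleed is overt bleeding "associated with a decrease in the hemoglobin level of 2 g/dL or more".

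**Creatinine clearance.** The Study Exclusion Criteria give "Serum calculated creatinine clearance (CrCl) < 25 ml/m at time of screening", and the CRF screening page has a matching checkbox, "Calculated creatinine clearance (CrCl) < 25 ml/m". The criterion under Subject Retention, Withdrawal, and Termination is stated in "mL/min confirmed by repeat testing at least one week later, or need for dialysis". The comorbidity page of the CRF has a field for the number itself, "creatinine clearance (Cockcroft-Gault" method), with a blank followed by mg/dL. That field comes after a yes/no item on serum creatinine above 2.5 mg/dL and a follow-up question on dialysis, and it is completed only after a no answer.

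**The concern.** Both quantities decide who may enter a study of an anticoagulant, so the limits need to be exact. A hemoglobin limit whose printed unit is wrong by a factor of 1000 is not an auditable rule. A monitor who applies the text literally would find every screened patient compliant, and one who silently corrects the unit is no longer checking against the protocol. The slip is also in the form that gates enrollment, so the form cannot serve as the correct copy.

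For clearance, a numeric field with a concentration unit invites entry of the wrong quantity, for example serum creatinine, which the same item quotes in mg/dL. If the field is skipped for some patients, the baseline table cannot report renal function for the whole cohort. The protocol's background section itself describes renal dysfunction as frequent in this disease.

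**Working it through.** The plan states no calculated figure on this point. The check is a unit conversion, a comparison of labels and a reading of the form's branches.

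**1. Hemoglobin conversion.** Inputs: the limit of 9 mg/dL (Study Exclusion Criteria and CRF) and the fall of 2 g/dL (Primary Safety Outcome).

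- 9 mg/dL ÷ 1000 mg per g = 0.009 g/dL.
- 9 g/dL ÷ 0.009 g/dL = 1000.
- 2 g/dL ÷ 0.009 g/dL ≈ 222.

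The fall that helps define a major bleed is about 222 times the literal entry limit. A patient at that limit could not have such a fall, so the two passages cannot both be right on units. Taken literally, the exclusion removes no one.

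**2. Clearance labels side by side.**

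| Place | Unit printed |
|---|---|
| Study Exclusion Criteria | ml/m |
| CRF screening checkbox | ml/m |
| Withdrawal criteria | mL/min |
| CRF value field, comorbidity page | mg/dL |

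The ml/m label is plainly a shortened flow unit. The mg/dL label is a different kind of quantity and cannot express a clearance.

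**3. Who gets a recorded clearance value.** The layout of this item was lost in text extraction, so the possible readings are set out separately.

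- (a) The no answer belongs to the dialysis question, which is the natural reading. The value is then recorded only for patients with creatinine above 2.5 mg/dL who are not on dialysis.
- (b) The no answer belongs to the creatinine question. The value is then recorded only for patients at or below 2.5 mg/dL.
- (c) Creatinine above 2.5 mg/dL itself bars enrollment. Every enrolled patient would then have a value. This is unlikely, because the dialysis question stands between that item and the do-not-enroll note, and the Study Exclusion Criteria contain no serum creatinine limit.

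**4. Does the 2.5 mg/dL gate match the clearance limit of 25?** The CRF names Cockcroft-Gault without printing the equation. I assume its usual form, (140 − age) × weight ÷ (72 × serum creatinine), times 0.85 for women, with ages 55 to 85 and weights 50 to 90 kg.

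- At creatinine 2.5, woman of 85, 50 kg: 55 × 50 × 0.85 ÷ (72 × 2.5) = 2337.5 ÷ 180 = 13.0 mL/min.
- At creatinine 2.5, man of 55, 90 kg: 85 × 90 ÷ 180 = 42.5 mL/min.
- Creatinine at which clearance equals 25: 2337.5 ÷ (72 × 25) = 1.30 mg/dL for the first patient, and 7650 ÷ 1800 = 4.25 mg/dL for the second.

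The gate therefore does not separate patients by the clearance limit. Under (a), patients eligible on clearance with creatinine at or below 2.5 have no value recorded. Under (b), an eligible patient above 2.5, such as the second one with creatinine up to 4.25, has none. On both main readings some enrollable patients lack a value.

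**The case against.** The strongest reply is that this is an evident slip with little practical effect. No clinician would apply 0.009 g/dL, the protocol uses g/dL for hemoglobin elsewhere, and no event rate, sample size or interval width depends on it. That stands as a limit on the consequence. It does not make the printed rule usable, and the slip appears in both the protocol and the enrollment form.

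Three stronger inferences are tempting, and the documents do not support them.

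- *Ineligible patients could slip through on clearance.* Take an assumed woman of 80, 50 kg, creatinine 1.8 mg/dL: 60 × 50 × 0.85 ÷ (72 × 1.8) = 19.7 mL/min. Under reading (a) her number is not entered. The screening page nevertheless has a clearance checkbox for every patient, followed by the instruction not to enroll, and Screening Procedures require confirmation that all exclusions are absent. She should be stopped there. The gap lies in the recorded value. The eligibility decision is recorded, and Study Completion requires source documents behind CRF responses.
- *Clearance is missing for most patients.* This holds only under reading (a). Under reading (b), patients at or below 2.5 mg/dL do have a value. The documents give no distribution of creatinine from which to estimate a proportion.
- *Withdrawal for declining renal function cannot be judged without a baseline.* The withdrawal trigger is an absolute level confirmed by repeat testing. It does not depend on a change from a recorded baseline.

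**Conclusion.** The point holds as a unit error in an operative entry criterion, printed in both the protocol and the CRF, together with a wrong unit on the CRF clearance field. The hemoglobin error is a factor of 1000, and the literal rule excludes nobody. These conclusions need no assumption beyond the printed text.

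That the clearance value is recorded for only some patients holds on both main readings of the form. It rests on reading (c) being unlikely, which the original page layout could settle. How many patients are affected cannot be stated from the documents.

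The practical effect is probably small. Staff would likely read the hemoglobin limit as g/dL, the clearance decision is captured for every patient, and the sample size of 50 and its stated precision are untouched. It is still worth correcting, because these are decision thresholds and the correction costs almost nothing.

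**What to change.** 1. Reconcile the hemoglobin unit between the Study Exclusion Criteria, the CRF screening page and the bleeding definition under Primary Safety Outcome.
2. Reconcile the clearance unit between the Study Exclusion Criteria, the CRF screening checkbox, the CRF value field and the withdrawal criteria.
3. Optionally, take the clearance value field out of the conditional branch so that it is completed for every screened patient.

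None of this proposes or changes a threshold; the numerical limits remain for the investigators to confirm. The cost is a few unit edits in the protocol and eCRF and, for the third item, removal of one skip rule. No new test is needed, because the exclusion criteria already require hemoglobin and calculated clearance at screening.
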